## 10. Assessment of Safety

## 10.1 Specification, Timing and Recording of Safety Parameters.

In each clinical recruitment site, patients will be asked to give blood samples for liver function (hepatotoxicity) testing during screening and monthly over the course of active treatment (weeks 4, 8 and 12). Samples will be analysed at the local hospital pathology service, with the following clinical biochemistry assays conducted: albumin, bilirubin, liver transaminases (AST/ALT (SGOT/SGPT) and transaminases.

Safety reporting will follow the requirements described in The Medicines for Human Use (Clinical Trials) Regulation 2004: SI 2004/1031 and the EU Directive 2001/20/EC. Each participant will be given a study identification (ID) card which describes the trial and provides the following information: some cough and cold medicines containing opiates may not work as well as they should and alternatives will be recommended; emergency pain relief following an accident may not be achieved using opiates; taking an extremely large dose of heroin to overcome NTX blockade could result in serious overdose; and there will be sensitivity to small doses of opiates after discontinuing NTX. The patient ID card will list telephone contact information to enable emergency unblinding. A 24-hour emergency code break will be available through ESMS, London.

All cause withdrawal from randomised treatment will be reported at months 1 and 3 post randomisation. The prevalence of specific adverse events and reactions will be reported descriptively at 1, 3 and 6 months post randomisation. Treatment stops at 3 months so adverse events and reactions recorded post this data will be specific to this follow up period (such as overdose, heroin lapse and relapse). The prevalence of patients experiencing one or more serious adverse events will be compared at 1, 3 and 6 months post randomisation across the three trial arms (as randomised) using Chi Square tests. Mortality prevalence will be considered independently to any other serious adverse events.

It is possible that the NTX implant procedure will lead to local site infection or other complications. Prophylactic anti-biotic medication can be used post-surgery and participants will be monitored and checked by the trial nurse on each clinic visit and by each centre PI (physician) each month. Site inflammation will be man managed on a case-by-case basis, and likely to involve steroidal anti-inflammatory treatment. All serious and non-serious adverse events identified after randomisation until 16 weeks post-randomisation will be reported, irrespective of causality.

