## 10.2 Procedures for Recording and Reporting Adverse Events

The Medicines for Human Use (Clinical Trials) Regulations 2004 and Amended Regulations 2006 gives the following definitions:

**Adverse Event (AE):** Any untoward medical occurrence in a participant to whom a medicinal product has been administered including occurrences which are not necessarily caused by or related to that product.

**Adverse Reaction (AR):** Any untoward and unintended response in a participant to an investigational medicinal product which is related to any dose administered to that participant.

**Unexpected Adverse Reaction (UAR):** An adverse reaction the nature and severity of which is not consistent with the information about the medicinal product in question set out in:

The summary of product characteristics (SmPC) for that product (for products with a marketing authorisation)

The Investigator's Brochure (IB) relating to the trial in question (for any other investigational product)

Serious adverse Event (SAE), Serious Adverse Reaction (SAR) or Unexpected Serious Adverse Reaction (USAR): Any adverse event, adverse reaction or unexpected adverse reaction, respectively, that

- Results in death;
- Is life-threatening;
- Required hospitalisation or prolongation of existing hospitalisation;
- · Results in persistent or significant disability or incapacity;
- Consists of a congenital anomaly or birth defect.

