#### **Reporting Responsibilities**

King's College London & South London and Maudsley NHS Foundation Trust have delegated the delivery of the Co-sponsors' responsibility for Pharmacovigilance (as defined in Regulation 5 of the Medicines for Human Use (Clinical Trials) Regulations 2004 to the King's Health Partners Clinical Trials Office (KHP-CTO).

All SAEs, SARs and SUSARs will be reported immediately (and certainly no later than 24hrs) by the Investigator to the KHP-CTO and CI for review in accordance with the current Pharmacovigilance Policy.

The adverse event form (AEF) will be reviewed at each trial assessment clinic visit (thrice weekly during weeks 1-12), at the 16, 24 and 36 week follow-ups, and following any occurrences in between study visits and follow-ups. All clinical investigators in the study will be provided with full details of possible adverse medical events that may result from the trial medication and/or procedure, as well as other possible occurrences that may not be caused by or related to that product or procedure.

Any adverse events occurring during the trial will be recorded in the participant's source data worksheet and filed in their medical records at the end of the trial. They will also be transcribed on to

the electronic Case Record Form (eCRF). A decision and reporting flowchart will be developed for the management of adverse events, and all research workers and investigators will receive training on safety issues and notification procedures.

Clinicians will report, and the centre Principal Investigator (PI) will assess, each adverse event for seriousness, causality (relationship to trial IMP: definitely related, likely, possibly, unlikely or not related), expectedness, and intensity (mild, moderate and severe). Copies of any SUSAR (suspected unexpected serious adverse reaction) will be sent to the Chair of the DMC. The centre PI (or clinician delegated to undertake this task) will sign the SAE report form on paper. The Trial Manager will manage SAEs outside the eCRF in order to comply with KHP-CTO procedures. The KHP-CTO CRA will issue queries on the SAE during monitoring visits to collect follow-up information until resolution of the event, and basic event information will be entered on the eCRF.

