## 12.4 Analysis

A comprehensive statistical analysis plan will be be developed and agreed with the trial's oversight committees.

There will be no planned interim analyses. An analysis of the data will be conducted once the trial database has closed. The Data Monitoring Committee will collate effectiveness and safety data during the trial to inform their recommendations to the Trial Steering Committee. A mid-trial formal data analysis is not envisaged.

Statistical analysis will be by intention-to-treat. Descriptive analyses (Q-Q plots, means and standard deviation, median and IQR, or numbers and proportions as appropriate) will be performed for the baseline variables and outcome variables, and will be described by treatment group. The time-to-event outcomes will be explored using life tables and survival plots (Kaplan-Meier curves).

The primary outcome analysis for the effectiveness of XR-NTX vs. placebo, and XR-NTX vs. O-NTX is described in Section 9.1. The secondary outcome analyses are described in Section 9.2.

In the case of missing assessments, such analysis can include these participants provided that prerandomisation values are available for the respective scales. The analysis presumes that the drop-out mechanism is missing at random (MAR). We will examine the scope for using multiple imputation (MI) to generate complete data records as a means of achieving greater efficiency and reduced missing data bias. We will also include as covariates in both model and MI any variables found to be associated with drop-out.

The significance level will be 2.5% (two-sided) for the primary outcome analysis and 5% (two-sided) for secondary outcome analysis. Group difference estimates and associated confidence intervals will be reported. The trial statistician will remain blind whenever possible until the main analyses have been completed.

Loss to follow-up, departures from randomized treatment and the prevalence of serious adverse events will be reported at 12, 16, 24 and 36 weeks post randomization.

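### Section 10.1 stops adverse event reporting at week 16, but the protocol compares serious events at 6 months and reports them at weeks 24 and 36

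*Protocol*

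**What the plan says.** Protocol Section 10.1 sets a between-arm test: "The prevalence of patients experiencing one or more serious adverse events will be compared at 1, 3 and 6 months post randomisation", by chi-square across the three arms as randomised. Deaths are handled apart: "Mortality prevalence will be considered independently to any other serious adverse events". It notes that treatment stops at 3 months and that events recorded later "will be specific to this follow up period (such as overdose, heroin lapse and relapse").

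The last sentence of Section 10.1 then sets a limit: "All serious and non-serious adverse events identified after randomisation until 16 weeks post-randomisation will be reported, irrespective of causality".

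Other parts of the protocol run longer:

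- Section 10.2, under Reporting Responsibilities, has the adverse event form reviewed three times a week during treatment, then "at the 16, 24 and 36 week follow-ups, and following any occurrences in between study visits and follow-ups".
- Section 12.4 states that "the prevalence of serious adverse events will be reported at 12, 16, 24 and 36 weeks post randomization".
- The schedule in Section 6.3 and the instrument list in Section 8.10 both mark the adverse event form as ongoing, with no end date.
- Section 9 gives the SAE reporting times as 1, 3 and 6 months after randomisation. That agrees with Section 10.1 but not with Section 12.4.

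**The concern.** The reporting window decides what sites send in. If they follow the 16-week sentence, serious events after week 16 may never reach the trial database, and no later analysis can recover them. The 6-month comparison and the 24- and 36-week reports would then be drawn up from an incomplete record, while a reader of the results would take them as complete to those dates.

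The missing stretch is clinically important. Dosing ends at week 12 and the implant is a 90-day product. Section 10.1 itself has patients warned that they will be sensitive to small opiate doses once naltrexone is discontinued, and it names overdose among the events it expects in follow-up. A limit at week 16 leaves only the first four weeks of that period within the reporting rule. Because adverse event definitions and windows govern collection at the sites, they belong in the protocol and are not a matter to settle in an analysis plan.

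**Working it through.** The protocol gives no computed figure for the safety comparison, so there is nothing of its own to reproduce. The check sets the stated windows side by side and counts the weeks.

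**Inputs**

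| Input | Value | Source (Protocol) |
|---|---|---|
| End of trial medication | week 12 | 6.4.3, 6.5.1 |
| Limit on reporting serious and non-serious events | week 16 | 10.1, last sentence |
| Any-SAE chi-square | months 1, 3 and 6 | 10.1 |
| Adverse event form reviewed | to week 36 | 10.2 |
| SAE prevalence reported | weeks 12, 16, 24 and 36 | 12.4 |

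There is no week-26 visit, so 6 months is taken two ways: the week-24 visit, or 26 calendar weeks.

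**Share of the period since randomisation left outside the limit** = (T − 16) / T

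- 6 months as week 24: (24 − 16) / 24 = 8/24 = 33%
- 6 months as week 26: (26 − 16) / 26 = 10/26 = 38%
- 36-week report: (36 − 16) / 36 = 20/36 = 56%

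**Share of the post-treatment period alone** = (T − 16) / (T − 12). This applies if the later counts cover only the time after treatment.

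- Week 24: 8/12 = 67%
- Week 26: 10/14 = 71%
- Week 36: 20/24 = 83%

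These are shares of calendar time. The protocol gives no event rates, so they are not shares of events.

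**Unaffected.** Months 1 and 3 fall before week 16, as do the week-12 and week-16 reports (the latter at the limit itself).

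**Two further inconsistencies found in the same check**

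1. The time points differ. Sections 9 and 10.1 use months 1, 3 and 6; Section 12.4 uses weeks 12, 16, 24 and 36. Month 1 has no counterpart in Section 12.4, and week 36 has none in Sections 9 and 10.1. Section 8.1 adds to the confusion. It lists follow-up at 1, 3 and 6 months where Section 6.2.4 lists weeks 16, 24 and 36. Those agree only if the months run from the end of treatment (12 + 4, 12 + 12, 12 + 24 weeks), whereas Section 10.1 counts from randomisation.
2. Section 10.1 does not say whether the 6-month count is cumulative. The remark that post-treatment events are specific to follow-up leans towards a separate count, but the sentence on the comparison makes no such split.

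**The case against.** The fairest defence is that the longer window is the working one. Section 10.2 requires SAEs to be sent within 24 hours and gives no end date, the form is reviewed at weeks 24 and 36, and the schedule calls it ongoing. On this reading the 16-week sentence was meant only for full all-cause reporting, perhaps of non-serious events, and serious events would have been captured anyway. Much of that is plausible, and it means that actual loss of data cannot be asserted. But the sentence names serious events explicitly and gives no rule for what follows week 16. Even if only treatment-related events were reported after that, an all-cause comparison at 6 months would be incomplete.

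A second defence also stands in part: toxicity during treatment is already tested at month 3, and the trial was wound down with 6 participants (Section 25.2), so no meaningful three-arm comparison will be made from it.

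A reader might go further and infer that relapse contaminates the SAE comparison: relapse is listed as an event, hospitalisation makes an event serious, inpatient detoxification exists at both centres, and so a detoxification admission would count as an SAE and hide toxicity. The documents do not support that step. The criterion "Required hospitalisation or prolongation of existing hospitalisation" is quoted as the regulatory definition, and the protocol nowhere says that an elective detoxification admission meets it. Inpatient detoxification appears in Section 7.3 as a recruitment source, not as care after relapse. The centre's principal investigator judges "each adverse event for seriousness, causality (relationship to trial IMP: definitely related, likely, possibly, unlikely or not related), expectedness" case by case, and the pharmacovigilance policy that governs reporting is not shown. The comparison is all-cause and is never presented as a measure of toxicity alone. Listing relapse among events to watch is reasonable after an antagonist stops. With no admission or SAE rates given, and no statement that the count is cumulative, a loss of power cannot be claimed.

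**Conclusion.** The conflict is real and rests on the text alone. Section 10.1 ends reporting at week 16, while Sections 9, 10.1, 10.2 and 12.4 plan comparison, review or reporting at 6 months, week 24 and week 36. If the limit governs, a third or more of the 6-month period (33% or 38%, depending on how 6 months is counted) and over half of the 36-week period (56%) have no reported events. If Section 10.2 governs, nothing is lost and the 16-week sentence is simply wrong. The protocol does not say which applies.

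The effect on any estimate is unknown, since it depends on late event rates that the protocol does not give. The earlier comparisons are sound. Given the closure, this is a modest point for the present trial. It matters chiefly for any future naltrexone implant trial that takes over the same wording, and Section 25 expects such trials.

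**What to change.** - In Section 10.1, replace the 16-week limit with reporting of SAEs, naming overdose and death as included, to week 36, in line with Sections 10.2 and 12.4. If a week-16 limit is wanted for non-serious events, say so, and restrict the 6-month descriptive table to the events still collected.
- Use one set of time points, in weeks from randomisation, in Sections 9, 10.1 and 12.4.
- State whether the 6-month count is cumulative from randomisation or covers only the time after treatment.
- Optionally, because lapse and relapse are named among post-treatment events, tabulate any SAE that is solely an elective detoxification admission separately, beside the all-cause comparison and not in place of it.

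The cost is a wording change in three sections and slightly more transcription after week 16. No visit or form is added, because the adverse event form is already reviewed at weeks 24 and 36. The optional table would need one judgement by the site for each such admission, with some risk of misclassification; keeping the all-cause comparison as the main one limits that risk.

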## 10.4 Treatment Stopping Rules

The trial may be prematurely discontinued by the Co-sponsors, Chief Investigator or Regulatory Authority on the basis of new safety information or for other reasons given by the Data Monitoring Committee / Trial Steering Committee regulatory authority or ethics committee concerned.

The trial may also be prematurely discontinued due to lack of recruitment or upon advice from a Trial Steering Committee (if applicable), who will advise on whether to continue or discontinue the study and make a recommendation to the sponsor. If the study is prematurely discontinued, active participants will be informed and no further participant data will be collected. The Competent Authority and Research Ethics Committee will be informed within 15 days of the early termination of the trial.

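### Section 10.1 limits adverse event reporting to week 16, which contradicts the protocol's later safety analyses and its own collection schedule to week 36; section 10.4 makes no safety exception on early closure

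*Protocol*

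**What the plan says.** **Reporting window.** The last paragraph of section 10.1 reads: "All serious and non-serious adverse events identified after randomisation until 16 weeks post-randomisation will be reported, irrespective of causality". It is the only place that puts an explicit end date on adverse event reporting.

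**Analysis times.** Earlier in section 10.1: "The prevalence of patients experiencing one or more serious adverse events will be compared at 1, 3 and 6 months post randomisation". Specific adverse events are to be described at the same three times, and overdose and return to heroin use are named as examples of what the post-treatment period may show. Section 9 also reports serious events at 1, 3 and 6 months after randomisation. Section 12.4 gives a different list: "the prevalence of serious adverse events will be reported at 12, 16, 24 and 36 weeks post randomization".

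**Collection schedule.** Section 10.2 (Reporting Responsibilities) has the adverse event form reviewed three times a week in weeks 1 to 12 and then "at the 16, 24 and 36 week follow-ups, and following any occurrences in between study visits and follow-ups". It has any adverse event during the trial recorded and transcribed to the eCRF, and it requires all serious events to be reported within 24 hours. None of these duties carries a week-16 limit. The schedule in section 6.3 and the instrument list in section 8.10 both mark the adverse event form as ongoing.

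**Early closure.** Section 10.4 says that if the study is discontinued prematurely, "active participants will be informed and no further participant data will be collected".

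**The concern.** A serious event comparison at 6 months, or a report at weeks 24 and 36, needs events to be reported up to those times in every arm. The week-16 sentence does not allow that, while section 10.2 does. A site could follow either text in good faith. If sites differ, prevalence after week 16 would mix complete and truncated reporting, and nothing in the protocol would show which was which.

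The weeks after week 16 matter for this drug. The patient ID card described in section 10.1 warns that "there will be sensitivity to small doses of opiates after discontinuing NTX", and documenting the safety of both naltrexone formulations is secondary objective D. Section 6.6 itself cautions that the published naltrexone safety record may be biased by incomplete adverse event data.

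Section 10.4 raises a related gap. Read literally, closure ends safety data collection even for a participant who still carries an implant. Section 25 records a wind-down decision in November 2016 with six participants recruited, so closure was not hypothetical.

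**Working it through.** The plan gives no figure of its own to reproduce here. The check compares the stated time windows.

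**Inputs**
- Reporting limit: week 16 (section 10.1)
- Study medication stops: week 12 (section 6.4.3)
- Implant period: 90 days (section 6.2), so 90 / 7 = 12.9 weeks
- 6 months after randomisation: 365.25 / 2 / 7 = 26.1 weeks
- End of follow-up: week 36 (section 7.6)

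**If the week-16 limit governs**

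| Target time | Weeks not covered | Share of time since randomisation | Share of time since week 12 | Share of time since end of implant period (XR-NTX arm) |
|---|---|---|---|---|
| Week 24 (12.4) | 24 − 16 = 8 | 8/24 = 33% | 8/12 = 67% | 8/11.1 = 72% |
| 6 months (9, 10.1) | 26.1 − 16 = 10.1 | 10.1/26.1 = 39% | 10.1/14.1 = 72% | 10.1/13.2 = 76% |
| Week 36 (12.4) | 36 − 16 = 20 | 20/36 = 56% | 20/24 = 83% | 20/23.1 = 86% |

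Covered time after the implant period: 16 − 12.9 = 3.1 weeks.

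**If sections 10.2, 8.10 and 6.3 govern**, uncovered time is 0 weeks at every target time. The range is therefore 0 to 20 weeks, depending only on which text a site follows.

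**Can the texts be read together?**
- *Serious events.* No. Section 10.1 says reported to week 16; section 10.2 says all reported within 24 hours, without limit. Both use the same verb.
- *Non-serious events.* Partly. One could record to week 36 under section 10.2 and report only to week 16 under section 10.1. That still leaves the description of specific adverse events at 6 months, in section 10.1 itself, without complete data.

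**Time labels.** Sections 9 and 10.1 use 1, 3 and 6 months; section 12.4 uses 12, 16, 24 and 36 weeks. Section 10.1 places the end of treatment at 3 months, so its months run from randomisation. Section 8.1 speaks of follow-up at 1, 3 and 6 months where section 6.2.4 gives weeks 16, 24 and 36. On either count the 6-month point (about week 26, or week 36) falls after week 16. Section 12.4 has no 1-month time at all.

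**The case against.** The strongest reply is that most of the protocol already keeps safety capture open to week 36, and one sentence should not be read as overriding the rest. This has force. An overdose that is fatal, life-threatening or leads to hospital admission meets the serious definition in section 10.2 and falls under the 24-hour rule at week 30 as much as at week 3. A reader might infer from the week-16 sentence that adverse events are collected only to week 16 and that later overdoses would be under-counted. The documents do not support that as a settled fact; it follows only if the sentence is applied.

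Three further inferences go too far:

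- *That the overdose hazard falls almost entirely after the implant's 90 days.* The documents do not say so, and it does not fit the other arms. Placebo participants enter with no opioid tolerance and never have blockade. Oral blockade lasts roughly 24 to 72 hours depending on dose (section 5), so it can lapse during weeks 1 to 12. Section 10.1 also warns of overdose from trying to overcome the blockade. The 3-week figure concerns the XR-NTX arm alone.
- *That serious events are compared between arms at week 36.* Section 12.4 only reports them then; the comparison across arms is at 1, 3 and 6 months.
- *That the lack of a 6-month visit, or the interviews in section 25, are defects in themselves.* Prevalence at 6 months can be derived from dated events collected at the week-36 review. Section 25 is a later qualitative study with its own approvals and does not show section 10.4 to be wrong.

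What remains is that the protocol fixes the reporting period itself, in two incompatible ways, and gives no rule for choosing. Nor does section 10.4 say that the duties in section 10.2 survive closure.

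**Conclusion.** The point holds as an internal contradiction, not as a fixed cut-off. Section 10.1's week-16 limit cannot stand beside its own 6-month comparison and description, the 6-month report in section 9, the week-24 and week-36 reports in section 12.4, or the collection schedule in sections 10.2, 8.10 and 6.3.

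The size is conditional. If the limit is applied, about 10 weeks before the 6-month comparison and 20 weeks before the end of follow-up go unreported, and the later serious event figures are incomplete. If section 10.2 is applied, nothing is lost. These figures take 6 months as 26.1 weeks and the implant period as 90 days; the documents give no event rates, so no number of missed events can be stated.

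The early-closure gap is separate and does not depend on which window governs. With six participants recruited, a between-arm test would tell little in practice, but the reporting period for those six and their safety follow-up after closure still need to be clear.

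**What to change.** 1. **Section 10.1, serious events.** Replace the week-16 limit so that serious adverse events, including overdoses and deaths, are recorded and reported to week 36 in all three arms, in line with section 10.2.
2. **Section 10.1, non-serious events.** Set their period to match the last time at which the plan describes them. Leaving it at week 16 while describing them at 6 months would keep the contradiction.
3. **Sections 9, 10.1 and 12.4.** Use one list of analysis times, counted from randomisation, and keep the early look at about 1 month, which is the first after the implant procedure. Weeks 4, 12, 16, 24 and 36 would do, since each already has a visit.
4. **Section 10.4.** State that early discontinuation does not end safety data collection for participants already randomised.

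The cost is a wording amendment and a few more serious event reports to process. The visits and adverse event reviews at weeks 24 and 36 are already in the schedule.
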